	
 2. The rate of detection of any disease site by ¹⁸F-fluciclovine PET/CT in the study population. 3. The rate of detection of 1) prostatic bed and other pelvic disease and 2) distant metastases (i.e., bone metastases, visceral metastases, or non-regional nodal metastases) with ¹⁸F-fluciclovine PET/CT in the study population. 4. The PPV of ¹⁸F-fluciclovine PET/CT to detect regionally recurrent disease compared to biopsy in those patients who undergo a regional disease biopsy on the basis of a ¹⁸F-fluciclovine PET/CT finding or in case of bony disease a correlation with MRI or biopsy. 5. The PPV of ¹⁸F-fluciclovine PET/CT to detect distant disease compared to biopsy in those patients who undergo a distant disease biopsy on the basis of a ¹⁸F-fluciclovine PET/CT finding or in case of bony disease a correlation with MRI or biopsy. 
An independent adjudication panel will review and adjudicate ¹⁸F-fluciclovine PET/CT lesions with biopsy or MRI during follow-up to assess the PPV and, where possible, NPV, sensitivity and specificity. Rates of disease detection (radiographic only and confirmed by pathology or MRI) will be described

Safety Evaluations	Monitoring for adverse events, change in EKGs and routine hematology and biochemistry evaluations taken prior to and following receipt of ¹⁸ F-fluciclovine
Planned Interim Analyses	An interim analysis of a subset of study results on all enrolled subjects may be submitted for potential public presentation prior to completion of all data collection and analyses. As trial design will not be modified as a result of this interim analysis, no adjustment to the type I error is required.
STATISTICS Primary Analysis Plan	For the evaluation of the primary endpoint (i.e., impact on therapy), questionnaires obtained pre- and post- ¹⁸ F-fluciclovine PET/CT will be compared to calculate the fraction of cases with a change in management (versus no change in planned management). The 95% confidence interval will be calculated using the Exact method for a binomial distribution.

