5.3 Safety Evaluations

1. Change from baseline QTc intervals and any clinically significant alterations in EKG after ^{18}F -fluciclovine PET/CT scanning
2. Change from baseline values in hematology and biochemistry profiles after ^{18}F -fluciclovine PET/CT scanning
3. Incidence of adverse events occurring after the ^{18}F -fluciclovine injection

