6.2.2 Biochemistry

Biochemistry values will be summarised by parameter and visit, and also for change from baseline (last pre-scan value vs first post-scan value).

Additionally, from the serum creatinine levels (mg/dL), creatinine clearance (CrCl) will be derived using the Cockcroft Gault formula (Cockcroft DW, 1976) and the glomerular filtration rate (GFR) will be derived using the modification of diet in renal disease (MDRD) formula (Levey AS, 2006) as follows:

- Cockcroft-Gault formula: $\text{CrCl (mL/min)} = (140 - \text{age}) * (\text{Weight in kg}) * (0.85 \text{ if female}) / (72 * \text{Creatinine})$
- MDRD formula: $\text{GFR (mL/min)} = 175 * \text{Creatinine}^{-1.154} * \text{age}^{-0.203} * 1.212$ (if subject is black) * 0.742 (if female)

CrCl and GFR categories (≤ 30 mL/min, $>30 - \leq 60$, $>60 - \leq 90$, >90 mL/min) will be summarised, and a shift table of baseline status against the status on or after ^{18}F -fluciclovine administration will be presented.

All biochemistry values will be listed showing reference ranges and flagging abnormal findings.

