6.4 Electrocardiography

Electrocardiogram (EKG) interpretation is recorded pre-dose/pre-scan and within 7 days of the scan. EKG observed QTc and change from baseline will be summarised by visit. In addition, a summary of the incidence of outliers in absolute QTc intervals (>450 , >480 and >500 msec), and the change from baseline in QTc intervals (>30 and >60 msec both positive and negative changes) will be presented.

The overall interpretation of the EKG (Normal, Abnormal NCS, and Abnormal CS) will also be summarised by visit. All EKG results will be listed, including overall interpretation and change from baseline.

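### SAP 6.4 summarises EKG interpretation only by visit, which cannot give the number of men with a new clinically significant abnormality after the scan

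*SAP*

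**What the plan says.** Item 1 of Protocol 5.3 (Safety Evaluations) has two parts: "Change from baseline QTc intervals and any clinically significant alterations in EKG after" the scan. The synopsis describes the same evaluation as a change: "Monitoring for adverse events, change in EKGs and routine hematology and biochemistry evaluations taken prior to and following receipt of" the tracer.

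SAP 6.4 sets out when the readings are taken: "Electrocardiogram (EKG) interpretation is recorded pre-dose/pre-scan and within 7 days of the scan". It then plans three things:

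- **QTc.** "EKG observed QTc and change from baseline will be summarised by visit", with counts of men above absolute thresholds and of men whose QTc moves by more than 30 or 60 msec in either direction.
- **Overall interpretation.** "The overall interpretation of the EKG (Normal, Abnormal NCS, and Abnormal CS) will also be summarised by visit".
- **Listing.** "All EKG results will be listed, including overall interpretation and change from baseline".

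Two other places bear on the point. SAP 6 says that safety tables count only subjects who have data. SAP 6.2.2 plans, for renal function categories, "a shift table of baseline status against the status on or after" administration. SAP 6.4 names no such table. SAP 3.5, which declares changes from the protocol's analysis, mentions only the PPV.

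**The concern.** An alteration is something that happens to one man between two readings. To count it, each man's post-scan interpretation has to be set against his own baseline. The by-visit table gives two separate distributions instead. A man who was Abnormal CS before the dose and is unchanged afterwards appears as Abnormal CS in the post-scan column, although nothing altered. A man who moves from Normal to Abnormal CS can be offset by another whose pre-dose abnormality clears.

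At stake is whether the clinical study report can state, from a planned summary, how many men developed a clinically significant EKG abnormality after the scan. Protocol 5.3 asks for that part of the evaluation separately from QTc (the other half of item 1) and from adverse events (item 3).

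**Working it through.** The plan gives no rate or count of EKG abnormalities, so there is no stated figure to reproduce. The check asks what a by-visit table leaves undetermined.

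**Set-up.** Take N men with both readings and classify each as Abnormal CS or not:

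- a = Abnormal CS at both readings
- b = Abnormal CS before only (resolved)
- c = Abnormal CS after only (new)
- d = Abnormal CS at neither

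The by-visit table reports x = a + b before the dose and y = a + c after it. The quantity wanted is c = y − a.

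**Bounds.** The overlap a is not reported. It can be as large as min(x, y) and as small as max(0, x + y − N). Therefore c lies between

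- lower: y − min(x, y) = max(0, y − x)
- upper: y − max(0, x + y − N) = min(y, N − x)

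**Numbers.** N = 330 is the maximum enrolment in Protocol 4.1, used here as if every man had both EKGs. The counts x and y are assumptions. The percentages use as denominator the N − x men who were not Abnormal CS at baseline, since only they can become newly so.

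| Abnormal CS before (x) | Abnormal CS after (y) | New cases consistent with the table | As % of N − x |
|---|---|---|---|
| 5 | 5 | 0 to 5 | 0 to 1.5% (5/325) |
| 10 | 10 | 0 to 10 | 0 to 3.1% (10/320) |
| 20 | 20 | 0 to 20 | 0 to 6.5% (20/310) |

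Within each row the by-visit table is identical across the whole range. If the totals differ, the lower bound rises but the answer is still not fixed: x = 5 and y = 10 give max(0, 5) = 5 to min(10, 325) = 10 new cases.

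**Denominators.** The bounds assume that the same N men stand behind both columns. SAP 6 does not guarantee this, because each column holds whoever has data. Note 3 to the protocol's Schedule of Events lets the post-dose EKG be done at another site within 7 days, so some men may lack it. A difference between the columns can then reflect who was measured.

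**Comparison within SAP 6.4.** The QTc half does not have this problem, because change from baseline and the 30 and 60 msec counts are calculated man by man. Only the interpretation half is left as two marginal distributions.

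**The case against.** The case on the other side is substantial, and most of it stands.

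- **The paired data will be reported.** The SAP lists every EKG result with its interpretation and change from baseline. In a single-arm study with one pre-dose and one post-scan reading, anyone can count new cases from that listing. This stands, so a reader who inferred that the information is lost would be wrong. But a listing of up to 330 men is not a planned number or percentage.
- **New findings may surface as adverse events.** The definition in Protocol 12.1 covers unfavourable signs whether or not they are related to the product, and SAP 6.1 tabulates treatment-emergent events up to 42 days after dosing. This stands in part. It depends on the investigator reporting the EKG finding as an event, and neither document has a rule linking an Abnormal CS reading to an adverse event report.
- **The table shells may contain a shift table.** SAP 1 puts the shells in a separate document, so this cannot be excluded. However, SAP 6.2.2 names its shift table in the text and SAP 6.4 names none.
- **The by-visit table does limit the damage.** New cases cannot exceed the post-scan Abnormal CS count when the same men are in both columns. A reader might infer that many new abnormalities could be hidden. That would need Abnormal CS readings to be common, and the documents give no rate.
- **The protocol does not define the event as a move between categories.** Protocol 5.3 says only "any clinically significant alterations in EKG after" the scan. Reading that as within-subject change is natural, but a move into Abnormal CS is one way of making it operational, not the protocol's definition. It also misses a man already Abnormal CS whose finding is different or worse afterwards.

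**Conclusion.** The point holds within narrow limits. For the clinically significant alteration half of Protocol 5.3 item 1, SAP 6.4 plans no summary that reports the count. The by-visit table it does plan is compatible with anything from max(0, y − x) to min(y, N − x) new cases, and its two columns may not describe the same men.

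A reader might infer more: that the SAP has dropped the protocol's EKG evaluation. The documents do not support that, since the QTc half is analysed as change from baseline and the interpretations are tabulated and listed.

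The algebra needs no assumption beyond men having both readings. The sizes in the table rest on assumed counts and should not be read as expected results. This is a minor safety-reporting improvement, with no effect on the sample size, the primary analysis or the conduct of the study.

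**What to change.** In SAP 6.4, keep the by-visit summary if wanted and add:

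1. A 3x3 shift table of baseline by post-scan interpretation (Normal / Abnormal NCS / Abnormal CS) in subjects with both EKGs, using the baseline already defined in SAP 6, and stating how many subjects lack one of the two readings.
2. The number and percentage of subjects newly Abnormal CS, with those not Abnormal CS at baseline as the denominator. An exact 95% CI is optional, since SAP section 6 plans no interval for any other safety variable.
3. A sentence saying that subjects Abnormal CS at both readings will be reviewed in the listing, and any whose finding is new or worse identified, because the shift table leaves them on the diagonal.

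The cost is one extra table and a few sentences of SAP text. Both readings are already scheduled, the SAP already uses a shift table for renal function, and neither new data nor a protocol amendment is needed. If the table shells already contain such a table, naming it in SAP 6.4 is enough for item 1.
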